3.6.8. Primary Endpoint

Primary endpoint of this study will be an assessment of the utility of FS and YE560 via survey of the operating surgeons.

24. The primary outcome will be response to the question “Based on the use and performance of FS in this case alone, how likely are you to use FS in future cases (excluding the research trial) involving this tumor?” We hypothesize that > 75% of responses will be “Plan to use in the majority of cases” or “Plan to use in all cases.”
25. This primary outcome will be supported by responses assessing correlation of FS with electrostimulation and visual assessment using light microscopy using Likert-style ratings. The responses to the latter correlation will be validated via presentation of fluorescence and white light microscopy images to the surgeons.

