3.1. Objectives

Primary objective of this initial feasibility study is to evaluate the benefit of using YE560 to visualize fluorescein sodium (FS) during surgery of VS, Meningioma, HNP, or HNS, determined from surgeon assessment.

Secondary objectives are:

- To evaluate the optimum FS dose and timing to be used with the YE560 device as determined by reported performance on surgeon surveys
- Quantify tissue differentiation of fluorescent VS and adjacent nerves using RGB image analysis
- To report clinical outcomes, including GTR rates, postoperative hearing outcomes, and postoperative facial nerve function

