3.2. Literature Review and Rationale

In VS cases where intervention is recommended, stereotactic radiosurgery and microsurgical resection offer two therapeutic options. Comparatively, microsurgical resection carries the advantage of offering the highest chance of a cure. The goal of surgery remains to resect the tumor while maintaining the integrity of the adjacent, and sometimes intimately adherent cochlear and facial nerves. Thus, gross total resection cannot always be achieved. Nakatomi and colleagues described the superior 15-year recurrence-free survival rates in patients receiving gross total resection (56%) versus subtotal resection (8%).¹ Intraoperatively, maximum resection of the tumor while preserving facial function and hearing relies on the ability to distinguish normal nerve tissue and tumor. Additional means of distinguishing these tissues could facilitate greater rates of gross total resection and preservation of cranial nerve function.

Intravenous FS has been used in ophthalmologic and neurosurgical applications to differentially cause fluorescence in tissues intraoperatively. This technique was reported in 1948 by Moore et al² and more recently by Koc and Toda in obtaining gross total resection of high grade gliomas^{3,4}. Fluorescein angiography has been routinely used for retinal imaging for vascular conditions and neoplasms since first described in 1961.⁵

As previously mentioned, two recent studies have demonstrated the application of intravenous FS to VSs. Perez et al have reported in vitro preferential uptake of FS in VS cells compared to native Schwann cells.⁶ Additionally, Pedro et al demonstrated feasibility of YE560 and intravenous FS in visualizing benign peripheral nerve sheath tumors—an identical histological entity to VS—located in the extremities.⁷ In our proposed study, the fluorescence light will be visualized with a surgical microscope (Kinevo 900) with YE560 fluorescence module. The device has optimized filter and optics; therefore, the concentration of fluorescein sodium per patient used in this study is expected to be lower than in earlier studies that do not use the fluorescence module.

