3.4. Hypothesis

12. Given prior evidence of preferential uptake of FS in VS and meningiomas due to disrupted blood brain barrier, we hypothesize that use of intravenous FS will allow for visual differentiation of tumor and surrounding structures and nerves using YE560.
13. The optimal dosing for FS has not been established for this application. Pedro et al utilized 0.5-1.0 mg/kg body weight to visualize peripheral nerve sheath tumors with YE560. The authors found saturation of all tissues with 3-4 mg/kg dose within 18 seconds of administration. The blood-brain barrier may play a modulating role. Schebesch et al (2013) used 3-4 mg/kg to visualize malignant gliomas and observed fluorescence after 20-30 minutes. We suspect that the optimal dose will be 3-4 mg/kg, and peak fluorescence will take a similar amount of time. However, we will initially utilize 1.0 mg/kg SF administered at the time of first visualizing the tumor to enable subsequent doses (up to a maximum of 500 mg or 7 mg/kg). This will allow us

to determine the minimum effective dose and observe the time to peak fluorescence. The optimal dosing strategy will be finalized after the first 10 cases.

14. We hypothesize that the surgeons will be satisfied with the use of SF and YE560, as reflected in responses on the Surgeon Survey. Specifically, we hypothesize that greater than 75% of surgeons would choose to use SF and YE560 at least in the majority of future VS, meningioma, HNP, or HNS resections based on responses from the Surgeon Survey. Secondarily, we hypothesize that surgeons will rate the correlation of fluorescence with visual assessment with white light microscopy and electrostimulation to be “good” or “excellent” for over 75% of the cases.
15. Because the yellow fluorescence is primarily comprised of red and green components, we hypothesize that RGB component analysis of intraoperative images will yield significantly higher red and green values in the VS compared to the facial and cochlear nerves. Similar analysis may be conducted between the tumor and surround nerves or structures of interest for meningiomas, HNP, and HNS.

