1. Fluorescein Sodium Administered: _____ ; corresponding event (e.g. opening dura): _____
 - a. If second dose given, time administered: _____, dose _____ mg/kg
 - b. If third dose given, time administered: _____, dose _____ mg/kg
2. Tumor first visualized: _____
3. Did the contrast between the tumor and normal tissue **change after initial visualization of the tumor?**
No change in Contrast over Time / Increased Contrast over Time / Decreased Contrast over Time
4. If there was a change in contrast over time, **when did peak fluorescence** occur such that there was maximum contrast between the tumor and normal tissue? _____
5. Did the tissue become **saturated** with fluorescein such that there was no difference in the fluorescence of nerve and tumor? Yes / No
 - a. If so, when did saturation occur? _____
6. When did the fluorescence diminish such that it was no longer useful _____ / Not Applicable

For the following questions, please circle one number in the boxes below.

7. How well did fluorescence **correlate with your visual assessment** of the tumor and nerve tissue under normal microscopy without the Yellow 560 filter?

No correlation 1	Some correlation 2	Good correlation 3	Excellent correlation 4
---------------------	-----------------------	-----------------------	----------------------------

8. How well did fluorescence **correlate with electrostimulation** (e.g. tissues with high fluorescence do not stimulate, whereas nerve tissues with low fluorescence do stimulate)?

No correlation 1	Some correlation 2	Good correlation 3	Excellent correlation 4
---------------------	-----------------------	-----------------------	----------------------------

9. How helpful was the use of FS and Yellow 560 filter in.... (circle a rating for each row)

	Not helpful at all	Minimally helpful	Somewhat helpful	Very helpful	N/A
Distinguishing tumor from normal nerve	1	2	3	4	0
Preserving facial nerve function	1	2	3	4	0
Preserving hearing	1	2	3	4	0
Detecting residual tumor	1	2	3	4	0

10. Based on the use and performance of FS in this case alone, **how likely are you to use FS** in future cases involving this tumor type (excluding the research trial)?

Unsure 0	Plan to not use in any cases 1	Plan to use in select cases 2	Plan to use in the majority of cases 3	Plan to use in all cases 4
-------------	--------------------------------------	-------------------------------------	--	-------------------------------

Comments for the research team: _____

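### The primary survey item asks about FS without naming YE560, so a result above 75% cannot be attributed unambiguously to FS with YE560

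*Protocol*

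**What the plan says.** Three statements in the protocol set out what the primary result should be about. Section 3.1 gives the primary objective as to "evaluate the benefit of using YE560 to visualize fluorescein sodium (FS) during surgery". Section 3.4 carries the threshold: the investigators expect that "greater than 75% of surgeons would choose to use SF and YE560 at least in the majority of future" resections of the listed tumor types. Section 3.6.8 opens with the label of the endpoint: "Primary endpoint of this study will be an assessment of the utility of FS and YE560 via survey of the operating surgeons".

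Section 3.6.8 then defines the primary outcome by one survey question. It first points to how FS was used and performed in the case just finished, and then asks "how likely are you to use FS in future cases (excluding the research trial) involving this tumor". The stated expectation is that more than 75% of responses fall in the top two categories (majority of cases, or all cases). Item 10 of the Surgeon Survey in Appendix 3 has the same content with slightly different word order. Neither version mentions the filter.

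Item 9 of the same form, directly above, does name both: "How helpful was the use of FS and Yellow 560 filter in", followed by four surgical purposes. Item 7 also names the filter.

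**The concern.** The objective, the hypothesis and the endpoint label are about a device, or a dye and a device together. The one question that is scored is about the dye. A surgeon who intends to keep using FS, but has no settled view on the filter, can truthfully choose one of the top two answers. That answer then counts toward a hypothesis about FS with YE560.

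This is the only stated primary outcome. The gap also lies in the data collection form, so an analysis plan cannot close it later: the answers will have been given to the narrower question.

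**Working it through.** The protocol attaches no significance level, power or expected rate to the 75% mark, so there is no figure of its own to reproduce. The check is a comparison of texts.

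**Step 1. What each place names.** (The protocol writes both FS and SF for fluorescein sodium.)

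| Place | Role | FS named | YE560 named |
|---|---|---|---|
| 3.1 | Primary objective | yes | yes |
| 3.4 | Hypothesis with the 75% mark | yes | yes |
| 3.6.8, opening sentence | Endpoint label | yes | yes |
| 3.6.8, question | Primary outcome | yes | no |
| Appendix 3, item 10 | Item as put to the surgeon | yes | no |
| Appendix 3, item 9 | Helpfulness ratings | yes | yes |

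The omission occurs both in the endpoint section and on the form, so it is not a slip in one place.

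**Step 2. The two clauses of the question.** The first clause concerns performance in the case just completed. Section 3.6.7 counts a patient in the study population only after YE560 visualization, and step 4 of section 3.6.11 has the module used to view the fluorescence. For this clause the filter is therefore implied. The second clause concerns intention in future cases outside the trial. Nothing in it requires the filter, and this is the part that is scored.

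**Step 3. Can dye and filter be separated?** Section 3.2 refers to "earlier studies that do not use the fluorescence module", so the protocol itself acknowledges FS use without the module. Item 9 shows that the form can name both when it means both.

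**Step 4. Direction and size.** Let p be the share of responses in the top two categories of item 10, and s the share of those favourable responses that express an intention to use FS but not FS with YE560. Anyone who plans to use FS with YE560 in most cases also plans to use FS in most cases. Read literally, then, the share for the combination is

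p × (1 − s), with s between 0 and 1.

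If s = 0 the two shares are equal. If s > 0 the item overstates acceptance of the combination. The protocol gives no value or range for s, so the calculation stops here.

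**The case against.** The strongest reply is that FS is shorthand here. The sentence just before the question defines the endpoint as the utility of FS and YE560. The item that follows it in section 3.6.8 speaks of correlating FS with electrostimulation, where survey item 8 speaks of fluorescence. A surgeon reaches item 10 immediately after rating the combination in item 9. The primary objective is itself about using YE560 to see FS, and section 6 notes that a contrast agent is required to obtain images. The remark in section 3.2 about studies without the module explains an expected lower dye concentration; it does not predict how these surgeons would work. The FS precedents cited for peripheral nerve sheath tumors and for meningioma both used YE560.

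Much of this stands. A reader might infer that the primary result says nothing about acceptance of the device. The documents do not support that, because the performance being rated was seen through YE560 in that same case.

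A reader might also want to count how many dye-only answers would bring a favourable result down to 75% or below. The documents do not support that either. They give no rate at which surgeons separate the two. Nor is the number of responses fixed at the 90 planned patients: section 3.6.11 has the operating surgeons, in the plural, complete the survey, and the form records the respondent's specialty. The study is described in section 3.5 as largely descriptive, and no decision rule is tied to the 75% mark.

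What the reply does not settle is the intention clause. Shorthand is a plausible reading, but the respondent has only the form, on which the filter is named in items 7 and 9 and dropped in item 10.

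**Conclusion.** The mismatch is confirmed. The primary item measures acceptance of FS with YE560 indirectly, and a result above 75% cannot be attributed unambiguously to the combination named in the hypothesis. On a literal reading any error is in one direction, toward overstating acceptance of the combination. Its size is unknown, and it may be nil if every respondent reads FS as FS seen through the filter.

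The conclusion rests on the wording alone. It assumes that the surgeon answers the printed question, and that using the dye without the module is possible, as section 3.2 acknowledges. It does not depend on the sample size or on any assumed response rate. The change is worth making because this is the sole primary outcome and answers already given cannot be reinterpreted.

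**What to change.** In section 3.6.8 and in item 10 of the survey, name FS with the YELLOW 560 filter in both clauses: once where the question refers to use and performance in this case, and once where it asks about future use. Item 9 already names both. The response categories and the 75% mark can stay as they are.

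If forms have already been completed with the present item 10, report them separately from those completed with the revised item, and do not pool the two without comment.

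Rewording the objective, hypothesis and endpoint label to concern FS alone would also make the passages agree, but the primary result would then no longer address the module that the study sets out to evaluate.

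The cost is one phrase in two places, with no added patients, visits or procedures. The one drawback is two wordings in the data set if enrollment is under way.

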3.5. Design and Proposed Analysis

16. The feasibility study will involve 90 patients, focusing on intra-operative visualization of fluorescein using YE560 in VS, meningioma, HNP, or HNS, inclusive of recurrent tumors, previously radiated tumors, and patients with neurofibromatosis type 2. There will be an allowance to enroll up to 95 patients to meet the goal of 90 subjects if subjects are withdrawn from the study due to a different pathologic entity diagnosed on biopsy of the tumor. Establishing the optimal dose and timing for FS will be a part of the feasibility study. Flexibility will be allowed with the dose and timing to achieve optimal visualization condition based on surgeon feedback with a maximum cumulative dose of 500 mg (standard dosage for ophthalmology angiography). The study will be largely descriptive, documenting the macroscopic appearance of FS and describing surgeon observations with regards to timing of peak fluorescence, correlation with electrostimulation, and utility in differentiating normal tissue from tumor.
17. Images containing the tumor and facial and cochlear nerves (or other relevant structures of interest in the case of meningioma, HNP, or HNS) will be captured with the microscope with the YE560 filter by the surgeon and analyzed; the YE560 filter will then be turned off and another identical image will be captured under white light microscopy for the separate survey validation analysis. For the RGB component image analysis, the fluorescence of the tumor will be measured in comparison to the facial nerve and cochlear nerve using ImageJ image analysis software to quantify the red, green, and blue components of the images. Inferential statistics will be used to compare the red, green, and blue components of regions of interest from the VS and the adjacent facial or cochlear nerve.
18. For the survey validation analysis, we will validate the question “How well did fluorescence correlate with your visual assessment of the tumor and nerve tissue under normal microscopy without the Yellow 560 filter?” The neurosurgeons and neurologists will be presented with 30-60 second videos of the VS and facial and/or cochlear nerves, with and without YE560 active. The surgeons will respond to the above question with choices of “no correlation,” “some

correlation,” “good correlation,” and “excellent correlation.” Other questions from the surgeon survey will not be validated due to the scope of the feasibility study.

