3.6.7. Point of Enrollment

Potential subjects will be provided with plain language information about the research on the informed consent form, prior to signing the consent form indicating their willingness to participate. The point of

enrollment shall be upon clinical evaluation and consent for surgery. The patient shall be considered as part of the study population once they have undergone the YE560 visualization during the indicated microsurgery with confirmatory histopathology. Patients will be withdrawn from the study population if their final histopathology is not consistent with vestibular schwannoma; this is expected to occur in less than 5% of subjects. Clinical data, intraoperative images, survey results and postoperative clinical data will still be maintained for these patients for potential case presentation or evaluation of bias.

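### The 75% benchmark for the primary outcome is an observed share with no allowance for uncertainty or repeat ratings, and sections 3.4 and 3.6.8 count it in different units

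*Protocol*

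**What the plan says.** The primary outcome is one item of the surgeon survey, on intended future use of fluorescein, answered for each case. Section 3.6.8 of the Protocol attaches one figure to it: "We hypothesize that > 75% of responses will be" in the top two categories (use in the majority of cases, or in all cases). The unit there is the response.

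Section 3.4 gives the same benchmark in another unit: "we hypothesize that greater than 75% of surgeons would choose to use SF and YE560" in most future resections, judged from the survey.

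On size and analysis, section 3.5 states "The feasibility study will involve 90 patients", with enrolment of up to 95 allowed so that 90 remain. It adds "The study will be largely descriptive". It mentions inference in one place only, the image analysis: "Inferential statistics will be used to compare the red, green, and blue components of regions of interest". No interval, test or error level is attached to the 75%, and 90 is not derived from it.

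The study runs at one institution (section 2.2). The operating surgeons complete a survey after each operation (section 3.6.11, step 13). Neither the number of surgeons nor the number of responses per case is fixed.

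**The concern.** The benchmark compares a percentage of responses with 75% and asks for nothing more. An investigator who follows the wording could report the primary hypothesis as borne out as soon as the observed share passes 75%, even when the data are compatible with a true rate well below it.

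Two features make this worse. First, surgeons at a single site will rate many cases each, so 90 responses carry less information than 90 independent opinions. Second, the benchmark has two units. A share of responses and a share of surgeons can fall on opposite sides of 75% in the same data, and no analysis can follow both sections. At stake is the conclusion drawn on the primary outcome.

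**Working it through.** **Inputs.** Benchmark 75% (sections 3.4 and 3.6.8); 90 patients (section 3.5). One independent response per patient is an assumption for steps 1 and 2. The Protocol gives no derivation of 90 and no error level, power or target precision, so there is no planned figure to reproduce.

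**Step 1: smallest count above the benchmark.** 0.75 × 90 = 67.5. 67/90 = 74.4% misses it; 68/90 = 75.6% meets it.

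**Step 2: what 68/90 shows.** The exact (Clopper-Pearson) 95% limits are the 2.5% quantile of Beta(68, 23) and the 97.5% quantile of Beta(69, 22), which are 65.4% and 84.0%. The lower limit is about 10 points below the benchmark. For the exact lower limit to exceed 75%, 76/90 (84.4%) is needed; that lower limit is 75.3%.

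**Step 3: repeat ratings by the same surgeon.** Let k be the number of surgeons, with equal caseloads of 90/k, and ρ the intraclass correlation. The design effect is 1 + (90/k − 1)ρ. The approximate half-width is 1.96 × √(0.75 × 0.25 / 90) × √(design effect). Without clustering it is 1.96 × √(0.1875/90) = 8.9 points. The values of k and ρ below are assumptions.

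| k | ρ | Design effect | Effective n | Half-width (points) |
|---|---|---|---|---|
| 8 | 0.05 | 1 + 10.25 × 0.05 = 1.51 | 59.5 | 11.0 |
| 8 | 0.2 | 1 + 10.25 × 0.2 = 3.05 | 29.5 | 15.6 |
| 4 | 0.05 | 1 + 21.5 × 0.05 = 2.08 | 43.4 | 12.9 |
| 4 | 0.1 | 1 + 21.5 × 0.1 = 3.15 | 28.6 | 15.9 |
| 4 | 0.2 | 1 + 21.5 × 0.2 = 5.30 | 17.0 | 20.6 |

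The half-width therefore runs from about 11 to about 21 points, against 9 under independence.

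**Step 4: the two units.** Take an invented case with four surgeons who have 35, 35, 10 and 10 cases. If the first two answer favourably every time and the other two never do, the share of responses is 70/90 = 77.8%, but only 2 of 4 surgeons (50%) are favourable. Conversely, if all four are favourable in 60% of their cases, the share of responses is 54/90 = 60%, yet every surgeon is favourable more often than not. The surgeon unit is also coarse: more than 75% means 4 of 4 surgeons, or 7 of 8.

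**The case against.** The strongest reply is that the Protocol contains no success rule. It states a hypothesis in a feasibility study that it calls largely descriptive, and no section says that the study succeeds or that benefit is declared above 75%. A hypothesis that a proportion exceeds 75% is compatible with a later test or interval, and a statistical analysis plan that is not shown here may supply one. This stands, and the absence of a test is not part of the point.

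It also disposes of a stronger reading. A reader might infer a pass/fail rule with a false-positive rate of about one half, since with 90 independent responses the chance of 68 or more favourable is 0.51 at a true rate of 75% (0.15 at 70%, 0.88 at 80%). The documents do not support this. They define no test to which an error rate could belong, and any cut-off judged at its own threshold is passed about half the time. The figure reveals no miscalculation in this Protocol.

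On the unit, it can be said that section 3.4 refers back to survey responses, so that its mention of surgeons may be loose wording. That is plausible, and it makes the repair easy. It does not remove the discrepancy, because the two sections as written name different denominators for the primary benchmark.

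The descriptive label does not fully answer the point either. A descriptive study can report a proportion, but once a numerical hypothesis is attached to the primary outcome, readers will ask whether it was met. The only inference that the Protocol mentions is for image colour.

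**Conclusion.** The point holds as one about wording and interpretation. The primary benchmark is an observed share with no allowance for uncertainty or for repeat ratings, and its unit differs between sections 3.4 and 3.6.8.

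Read literally, it is met by 68/90, a result compatible with true rates from 65.4% to 84.0%. That interval assumes 90 independent responses. The clustered half-widths of about 11 to 21 points rest on assumed numbers of surgeons, equal caseloads, assumed correlations and a normal approximation that is rough at small effective sample sizes. The difference in unit rests on the text alone.

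Nothing here shows that the study would make a false declaration of benefit or that 90 patients is the wrong number.

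**What to change.** 1. Use one unit, the response, in sections 3.4 and 3.6.8.
2. In section 3.6.8, state that the favourable proportion will be reported with a 95% interval that allows for repeat ratings by the same surgeon.
3. Add that the rate will be said to exceed 75% only if the lower limit does; otherwise the proportion is presented as an estimate.

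This takes a few sentences. It needs no extra patients, but the responding surgeon must be identifiable by a code: the survey form in Appendix 3 has a field for the respondent's specialty and none for the individual.

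The downside is that a result just above 75% can no longer be described as confirming the hypothesis. With independent responses, 76/90 would be needed for that statement. With clustering the count rises: with 4 surgeons and a correlation of 0.1, about 79/90 (87.8% − 1.96 × √(0.878 × 0.122 / 28.6) = 75.8%, whereas 78/90 gives 74.2%). The same approximate formula gives 76/90 with 8 surgeons and 0.05, and 81/90 with 4 surgeons and 0.2. This governs only the claim that the rate exceeds 75%; it does not set a bar that the feasibility study has to pass.
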